6.5.2 Thromboprophylaxis

An anticoagulant (eg, enteric-coated aspirin at standard prophylactic dose or other anticoagulant or antiplatelet medication such as clopidogrel bisulfate, low molecular weight heparin, or warfarin), is a suggested concomitant medication in subjects based on an individual benefit/risk assessment (Li et al, 2016).

6.5.3 Tumor Lysis Syndrome Prophylaxis

An approved uric acid-lowering agent (eg, allopurinol) in subjects at high risk for tumor lysis syndrome (TLS) due to high tumor burden may be prescribed at the investigator's discretion, according to the package insert.

Subjects should be well hydrated to reduce the risk of TLS and decline in renal function; refer to the current Carfilzomib IB for safety guidance regarding TLS.

6.5.4 Proton-pump Inhibitor

Proton-pump inhibitor (omeprazole or equivalent) is required while on dexamethasone.

6.5.5 Bone Health Therapy

Concomitant bone health therapy is strongly recommended for all subjects with evidence of lytic destruction of bone or with osteopenia (Terpos et al, 2013; Gralow et al; 2013). Commercially available therapies are preferred when available, and should be used according to the manufacturer's recommendations, as described in the prescribing information, for subjects with osteolytic or osteopenic myelomatous bone disease.

Subjects who are using bisphosphonate or monoclonal antibody therapy when they enter the study should continue the same treatment. Subjects with evidence of lytic destruction of bone or with osteopenia who are not using a bisphosphonate or monoclonal antibody at the time of randomization should start a bisphosphonate or other bone health medications that have proven efficacy such as monoclonal antibodies as soon as possible during cycle 1 or 2 of treatment. Investigators should not start bisphosphonate or monoclonal antibody therapy during the study, unless it has been agreed with the sponsor that there is no sign of disease progression.

6.5.6 Prophylaxis for Pneumocystis Jirovenci

Pneumocystis jirovenci pneumonia (PJP) prophylaxis should be considered, as per institutional guidelines while on dexamethasone.

6.5.7 Prophylaxis for Hepatitis B Virus

Hepatitis B virus reactivation prophylaxis should be considered for subjects at risk (ie, subjects who test positive on serology or have a prior history of HBV infection) as per institutional standards.

6.5.8 Other Permitted Therapies

The following medications and supportive therapies are examples of support therapies that may be used during the study:

- antivirals
- hyperglycemia medical management
- prevention of constipation (eg, adequate hydration, high-fiber diet, and stool softeners, if needed)
- prophylactic antiemetics, with the exception of corticosteroids
- colony stimulating factors, erythropoietin, and transfusion of platelets and RBCs
- loperamide is recommended for the treatment of diarrhea, starting at the time of the first watery stool. The loperamide dose and regimen is according to institutional guidelines. Prophylactic loperamide is not recommended.
- adequate hydration is recommended for prevention of myeloma-related kidney disease
- intravenous immunoglobulins may be given at the discretion of the investigator according to local guidelines, eg, where low serum IgG concentrations may result in recurrent upper respiratory tract infections

6.6 Hepatotoxicity Stopping and Rechallenge Rules

Refer to [Table 4](#) (carfilzomib), [Section 6.2.2.2](#) (daratumumab), and [Table 9](#) (dexamethasone) for stopping and rechallenging requirements when subjects have abnormal hepatic laboratory values (ie, alkaline phosphatase, AST, ALT, total bilirubin) and/or international normalized ratio (INR) and/or signs/symptoms of hepatitis.

For subjects who are diagnosed with HBV reactivation while on daratumumab treatment, study treatment should be interrupted until the infection is adequately controlled (see [Section 6.7.1](#)).

6.7 Concomitant Therapy

Throughout the study, investigators may prescribe any concomitant medications or treatments deemed necessary to provide adequate supportive care except for those listed in [Section 6.9](#). Concomitant therapies are to be collected from informed consent, through 30 days following the last dose of all study drug(s).

For concomitant therapies being taken for the disease under study (eg, pre/post-infusion medications), collect therapy name, indication, dose, unit, frequency, route, start dates, and enter in the subject's eCRF.

For all other concomitant therapies (eg, those listed in Section 6.4.1), collect therapy name, indication, dose, unit, frequency, route, start and stop dates, and enter in the subject's eCRF.

It is recommended to follow the Eighth Joint National Committee 2014 evidence-based guideline for the management of high blood pressure in adults (James et al, 2014 and Appendix H). For elderly subjects, it is recommended to implement the 2013 ESH and ESC guidelines (Mancia et al, 2013 and Appendix I).

Any patient presenting at screening with a blood pressure outside parameter is suggested to have consultation with the institution's hypertension service for treatment recommendation.

6.7.1 Management of Hepatitis B Virus Reactivation

Local hepatitis B testing (HBsAg, anti-HBs, and anti-HBc) will be performed at the next scheduled visit for all subjects that do not already have a **known** medical history of hepatitis B infection or who have not had testing conducted within the previous 12 weeks.

Subjects with **evidence of positive HBV serology or who have a known history of HBV infection** should have consultation with a specialist in HBV and **be monitored for clinical signs of HBV reactivation with HBV DNA testing** every 12 weeks (\pm 2 weeks) or more frequently as clinically indicated **during and for 30 days following the last dose of all study drug(s)** (follow-up visit 1). **Thereafter**, subjects in arm 1 (KdD) will continue to be monitored and **have HBV DNA testing for a maximum of 6 months** following last dose of daratumumab. Subjects that have received Hepatitis B vaccination with only anti-HBs positivity and no clinical signs of hepatitis do not require HBV DNA testing and monitoring.

Any subject who becomes HBV DNA positive or develops reactivation of HBV will have study treatment interrupted and **a hepatitis specialist should be consulted to undergo full assessment and make decisions regarding HBV reactivation treatment and/or confirmation whether HBV reactivation is adequately controlled to resume study drugs. In consultation with the investigator, the hepatitis specialist may consider and advise** resumption of study treatment in subjects whose

HBV reactivation is controlled and where the benefits of study treatment outweigh the risks. After cessation of study therapy for any reason, any ongoing monitoring, testing, and anti-viral treatment should be under the guidance of a specialist in HBV.

6.8 Product Complaints

A product complaint is any written, electronic or oral communication that alleges deficiencies related to the identity, quality, durability, reliability, safety, effectiveness, or performance of a drug(s) or device(s) after it is released for distribution to market or clinic by either Amgen or by distributors and partners for whom Amgen manufactures the material.

This includes any drug(s), device(s) or combination product(s) provisioned and/or repackaged/modified by Amgen. Drug(s) or device(s) includes investigational product.

- carfilzomib
- daratumumab

Any product complaint(s) associated with an investigational product(s) or non-investigational product(s) or device(s) supplied by Amgen are to be reported.

6.9 Excluded Treatments and/or Procedures During Study Period

Concurrent therapy with a marketed or investigational anticancer therapeutic or radiation to large marrow reserves for either a palliative or therapeutic intent is excluded.

Long-term corticosteroids for nonmalignant conditions (eg, asthma, inflammatory bowel disease) equivalent to a dexamethasone dose > 4.0 mg/day or prednisone > 20 mg/day are not permitted. Corticosteroids given short-term (up to 2 weeks) for non-malignant conditions are permitted provided that the cumulative dose is less than 40 mg per week dexamethasone equivalent. Medical monitor should be contacted in the event that short-term corticosteroid use is required greater than 2 weeks or at cumulative dose of more than 40 mg dexamethasone equivalent.

Vaccination with live attenuated vaccines is not permitted at any time while the subject is receiving study treatment. Plasmapheresis is not permitted at any time while the subject is receiving study treatment. For subjects requiring plasmapheresis while on study treatment, every attempt should be made to document disease status by IMWG criteria first. Study treatment must be discontinued, and the subject will enter LTFU.

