3. EXPERIMENTAL PLAN

3.1 Study Design

This is a phase 3 multicenter, open-label, randomized study in subjects with RRMM who have received 1 to 3 prior therapies.

Subjects will be randomized in a 2:1 ratio to 1 of 2 arms:

- Arm 1: KdD using 20/56 mg/m² carfilzomib and 16 mg/kg daratumumab
- Arm 2: Kd using 20/56 mg/m² carfilzomib

Randomization will be performed using an interactive voice/web response system (IxRS) and subjects will be stratified based on the following criteria:

1. Original International Staging System (ISS) stage (variables: albumin and beta 2 microglobulin; strata: Stage 1 or 2 vs Stage 3) at screening
2. Prior proteasome inhibitor exposure (yes vs no)
3. Number of prior lines of therapy (1 vs ≥ 2)

4. Prior CD38 antibody therapy (yes vs no)

Subjects will receive the **study** treatment determined by randomization [REDACTED], or until confirmed disease progression, unacceptable toxicity, withdrawal of consent, or death (whichever occurs first). No crossover between the treatment arms will be allowed. All subjects will be assessed for multiple myeloma disease response according to the International Myeloma Working Group-Uniform Response Criteria (IMWG-URC) ([Appendix M](#)) using central laboratory test results every 28 ± 7 days. [REDACTED], disease response assessments will be performed every 28 ± 7 days until confirmed PD irrespective of cycle duration including dose delays or treatment discontinuation. [REDACTED].

Following progression or discontinuation of study drug(s), subjects will have **1** follow-up visit **30 days (+3)** after last dose of all study drug(s). **After disease progression**, data on survival **status** and subsequent antimyeloma therapy will be gathered at [REDACTED].

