6.2.1.3 Carfilzomib: Dose Reduction Levels

Dose reduction levels of carfilzomib for toxicity management of individual subjects are provided in [Table 2](#). Subjects that require a dose level reduction and tolerate the reduced dose for 1 full cycle, may at the discretion of the treating physician increase the dose to a prior dose starting with the next cycle except when the dose reduction is due to: pulmonary hypertension, pulmonary toxicity, grade 3 or worse cardiac failure, and drug-induced hepatotoxicity.

Table 2. Dose Decrements for Carfilzomib

Dose ^{a, b} (mg/m ²)	First Dose Reduction Dose -1 (mg/m ²)	Second Dose Reduction Dose -2 (mg/m ²)	Third Dose Reduction Dose -3 (mg/m ²)	Fourth Dose Reduction Dose -4 (mg/m ²)
56	45	36	27	20

CxDx = cycle X day X

^a If dose reduction of carfilzomib is required on C1D1 or C1D2, the investigator should contact the medical monitor to discuss the situation, before any additional doses of carfilzomib are administered.

^b For patients with baseline chronic hepatic impairment (mild, moderate), reduce the starting and subsequent doses of carfilzomib by 25% (ie, 15 mg/m² day 1 and 2 of cycle 1 and 42 mg/m² day 8 cycle 1 and thereafter).

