Footnotes defined on the next page of the table

Table 4. Dose Modification Guidelines for Nonhematologic Toxicities

Symptom/Sign/Investigation	Recommended Action
Progressive Multifocal Leukoencephalopathy	Patients should be monitored for any new or worsening neurologic, cognitive, or behavioral signs or symptoms that may be suggestive of PML as part of the differential diagnosis of CNS disorders. If PML is suspected, withhold administration of carfilzomib; patients should be promptly referred to a specialist and appropriate diagnostic testing should be initiated. Discontinue carfilzomib if PML diagnosis is confirmed. If the diagnosis is excluded, carfilzomib can be restarted at the same dose.
Thrombotic microangiopathy: Fever, microangiopathic hemolytic anemia, renal failure, thrombocytopenia, neurological manifestations	If the diagnosis is suspected, hold carfilzomib and manage per standard of care including plasma exchange as clinically appropriate. If TMA is confirmed, permanently discontinue carfilzomib. If the diagnosis is excluded, carfilzomib can be restarted at the same dose .
Venous thrombosis (≥ grade 3)	Hold carfilzomib and adjust anticoagulation regimen; resume at full dose once anticoagulation has been optimized per treating investigator's discretion.
Any other drug-related nonhematologic toxicity ≥ grade 3 ^b	For carfilzomib attribution, hold dose. Resume at 1 dose decrement when toxicity has resolved to grade 1 or less or to baseline grade.

Page 3 of 3

ALT = alanine aminotransferase; ANC = absolute neutrophil count; ARDS = acute respiratory distress syndrome; AST = aspartate aminotransferase; **CNS = central nervous system**; CrCl = creatinine clearance; DBP = diastolic blood pressure; LDH = lactate dehydrogenase; MRI = magnetic resonance imaging; NCI-CTCAE = National Cancer Institute-Common Terminology Criteria for Adverse Events; **PML = Progressive Multifocal Leukoencephalopathy**; PRES = Posterior Reversible Encephalopathy Syndrome; SBP = systolic blood pressure; TMA = thrombotic microangiopathy; ULN = upper limit of normal.

^a For a rapid fall from baseline in CrCl or an absolute fall of ≥ 60 mL/min, contact the medical monitor.

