FISH = fluorescence in-situ hybridization; HBV = hepatitis B virus; IAT = indirect antiglobulin test; K = carfilzomib; LTFU = long-term follow-up; LVEF = left ventricular

ejection fraction; MRD = minimal residual disease; PD = progressive disease; ██████████ PFT = pulmonary function test; PK = pharmacokinetics;

QTc = corrected QT (interval); SAE = serious adverse event.

^a Follow-up occurs: 30 days (+ 3) after the last administration of all study drug(s).

Table 12. Schedule of Disease Assessments

Assessment	Screening	Every 28 Calendar Days ^a (Starting From C1D1)	If Clinically Indicated	To Confirm PD	Notes
Disease Assessments					
Bone marrow sample for FISH and MRD[-]:	X	(X)			See Section 7.3.21.2 for additional timing details regarding FISH and MRD[-] assessments. Samples for MRD analysis are not required [REDACTED]
Bone lesion assessment	X		X	X	Within 30 days prior to randomization; will be repeated if worsening clinical symptoms suggest PD, or as clinically indicated.
Plasmacytoma evaluation	(X)	(X)	X	X	Will be done at screening only if clinically suspected. Screening evaluation may be done within 30 days prior to randomization, if performed as a part of standard of care. Assessment will be performed locally every 28 days (for physical exam) or every 12 weeks (for radiological exam).
SPEP/UPEP/immunofixation	X	X			Screening values may be used if within 14 days prior to C1D1. Post C1D1, UPEP and urine immunofixation will be measured every disease assessment.
SFLC	X	X			

(X) = Parentheses indicate that the particular test is situational at that time point, as specified in the respective notes.

CxDx = Cycle X day X; **DCO = data cutoff**; FISH = fluorescence in-situ hybridization; MRD = minimal residual disease; **OS = overall survival**; PD = progressive disease; PR = partial response; SFLC = serum free light chain; SPEP = serum protein electrophoresis; UPEP = urine protein electrophoresis.

^a [REDACTED], disease assessment should be performed every 28 ± 7 days until PD regardless of cycle duration including dose delays. Subjects who discontinue treatment prior to PD, but remain on study are required to complete the following assessments every 28 ± 7 days until PD. [REDACTED]

Table 13. Dosing Schedule - Arm 1 (KdD)

Investigational Products and Other Protocol-required Therapies	Dosing Cycle Day							Notes
	1	2	8	9	15	16	22	
IV predose and postdose hydration (for carfilzomib as needed)								

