7.2.5 Long-term Follow-up

Survival information and information on subsequent antimyeloma therapies will be collected during LTFU as listed in the Schedule of Assessments ([Table 11](#)) via a phone

call to subject every 12 weeks (\pm 2 weeks). Details of these procedures can be found in Section 7.3.

Arm 1 (KdD) **subjects with evidence of positive HBV serology or** with a known **medical** history of HBV infection **will be monitored for clinical signs and** local HBV DNA **testing for a maximum of** 6 months following the last dose of daratumumab (see Section 7.3.15).

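### Section 6.9's plasmapheresis rule conflicts with the Table 4 TMA row on treatment and with the until-progression assessment rule on follow-up

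*Protocol*

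**What the plan says.** **Section 6.9, Protocol.** "Plasmapheresis is not permitted at any time while the subject is receiving study treatment". If a subject needs the procedure, the site is asked to record response status beforehand ("every attempt should be made to document disease status by IMWG criteria first"), and then: "Study treatment must be discontinued, and the subject will enter LTFU". No progression is required for this step, and nothing is said about later disease assessments.

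**Table 4, TMA row (Protocol 6.2.1.5).** When TMA is suspected, sites are to "hold carfilzomib and manage per standard of care including plasma exchange as clinically appropriate". Confirmed TMA ends carfilzomib permanently; if TMA is ruled out, carfilzomib may resume. The row does not mention daratumumab. Sections 6.2.1.2 and 6.2.2.2 count a subject as on treatment while either investigational product is being taken, and 6.2.2.2 gives daratumumab its own hold, restart and discontinuation criteria.

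**Follow-up.** Section 3.1 has disease assessments run "until confirmed PD irrespective of cycle duration including dose delays or treatment discontinuation". Table 12, footnote a, adds: "Subjects who discontinue treatment prior to PD, but remain on study are required to complete the following assessments every 28 ± 7 days until PD". Sections 3.5.1, 7.2.4 and 7.3.21 agree. Section 7.2.5 describes long-term follow-up differently: "Survival information and information on subsequent antimyeloma therapies will be collected during LTFU", by telephone every 12 weeks, with hepatitis B monitoring for some arm 1 subjects. The LTFU column of Table 11 has the same content.

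**SAP Table 1.** A subject alive without documented progressive disease (PD) is censored at the last disease assessment. PD or death more than 70 days after the previous assessment is also censored.

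**The concern.** Section 6.9 is the specific instruction for these subjects, and it meets two others that do not fit it.

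On treatment, a site managing suspected TMA may use Table 4 and plan to resume or continue a drug, or may use 6.9 and stop everything. Neither passage refers to the other, so similar subjects may be handled differently between sites. In arm 1 the difference reaches daratumumab, the drug under test.

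On follow-up, a subject without PD is sent to a phase that lists no SPEP, UPEP or SFLC, although the general rule requires these until PD. If a site stops them, the subject leaves PFS follow-up because of a complication rather than at random. That makes the censoring possibly informative for the primary endpoint.

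**Working it through.** **1. Treatment rules side by side.** This takes plasma exchange and plasmapheresis as one procedure, which is an assumption.

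| Exchange given for suspected TMA | Table 4 with 6.2.1.2 and 6.2.2.2 | Section 6.9 |
|---|---|---|
| While suspected | Exchange accepted; carfilzomib held; daratumumab under its own hold criteria | Not allowed on treatment; all study treatment stops |
| TMA excluded | Carfilzomib may resume | No resumption provided for |
| TMA confirmed, arm 1 | Carfilzomib ends; daratumumab not mentioned in the row and may restart after recovery under 6.2.2.2 | All study treatment stops |
| TMA confirmed, arm 2 | Carfilzomib ends | All study treatment stops |

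The first three rows conflict. For confirmed TMA the two sources agree on carfilzomib.

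**2. Follow-up rules side by side.** Sections 3.1, 3.5.1, 7.2.4, 7.3.21 and Table 12 call for assessment every 28 ± 7 days until PD after treatment stops. Section 6.9 names LTFU as the next phase, and neither 7.2.5 nor Table 11 lists a disease test there. Section 6.9 does not say whether the 28-day schedule runs alongside.

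**3. Consequence under the literal reading.** With no disease tests, PD would not be documented. A death up to 70 days after the last assessment would still count as an event; a later one would not, and the subject would be censored at the last assessment. The SAP Table 3 sensitivity analysis for loss to follow-up or withdrawn consent does not cover these subjects, who are neither. The missing-assessment analysis might, but as printed it names the Kd arm for both of its rules.

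**4. Size.** Inputs from Protocol 10.2 and SAP 3.2: 188 events, HR 0.6, one-sided 0.025, 300 versus 150 subjects.

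Power = Φ(√(D × 2/3 × 1/3) × |ln HR| − 1.960)

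- D = 188: √(188 × 2/9) = 6.464; 6.464 × 0.5108 = 3.302; 3.302 − 1.960 = 1.342; Φ = 0.910. This reproduces the plan's claim of at least 90%.
- Minimum detectable HR = exp(−1.960/6.464) = 0.738, as stated.
- Exactly 90% power needs 182 events by the same formula, so 188 leaves a margin of 6.

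The documents give no frequency for plasmapheresis. The shares below are assumptions, with subject counts rounded down and lost events not replaced. The last column assumes that 188/450 = 42% of those subjects would have had an event.

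| Share of 450 | Subjects | Power, one event lost each | Power, 42% lose an event |
|---|---|---|---|
| 0.5% | 2 | 0.9073 | 0.9090 |
| 1% | 4 | 0.9043 | 0.9077 |
| 2% | 9 | 0.8965 | 0.9046 |
| 5% | 22 | 0.8734 | 0.8961 |

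The primary analysis is triggered by the event count, so uncounted events would mainly delay it. The table therefore overstates the effect on power.

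**The case against.** **Section 6.9 does not end disease assessment.** A reader might infer that PFS follow-up is lost under 6.9. The text does not say so: it contains no waiver, and the until-PD rule elsewhere is general. SAP 3.1, written for Amendment 4, places subjects in LTFU after progression or after stopping study drug, and SAP 9.2 counts a long-term follow-up phase before progression separately from survival follow-up. Assessments and LTFU calls can therefore run in parallel. This stands, and the loss is a risk of one reading only. However, the protocol describes no pre-progression LTFU phase with disease tests, and current Section 3.1 ties survival data collection to the period after progression, so sites have reason to misread it.

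**Response status is recorded first.** Section 6.9 asks for this, which limits the damage at the time of stopping but does not replace later assessments. It also suggests, by inference, doubt about M-protein values after the procedure. Continued assessment would need a rule for that.

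**The treatment conflict may be narrower than it looks.** The two procedure terms are never equated. Table 4 is carfilzomib guidance, so a reader might infer that it keeps arm 1 subjects on daratumumab, but the row is silent on that drug and 6.2.2.2 may require a hold. One could also argue that a subject with all drugs held is not receiving study treatment. These points stand, but they leave the possible carfilzomib restart and the status of daratumumab unresolved.

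**Censoring may occur anyway.** A subject who starts new antimyeloma therapy before PD is censored under SAP Table 1 however 6.9 is read. That reduces the added effect on the primary analysis.

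**The primary analysis is past.** The Amendment 6 rationale says that the primary endpoint has been met and that disease assessment moves to local standard of care (timing redacted). Section 7.3.21 says local values are not entered in the eCRF. New wording cannot recover primary PFS data.

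**Conclusion.** The concern holds as two inconsistencies that need reconciling. First, if the two procedures are the same, 6.9 and the Table 4 TMA row cannot both be followed. The conflict still applies to subjects on treatment. Second, 6.9 directs subjects without PD to a phase whose protocol description has no disease assessments, against the until-PD rule. A literal reading could stop PFS follow-up and lead to possibly informative censoring.

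The size is small or unknown. Under the assumed shares of 0.5% to 2%, power stays between 0.8965 and 0.9090 even without replacement of events. The issue is possible bias and inconsistent site conduct, not power.

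A reader might also infer that LTFU collects survival only, or that the affected subjects are a high-risk group. The documents support neither: LTFU also collects subsequent therapy and some hepatitis B data, and no passage describes the prognosis of these subjects. With the primary endpoint met, the PFS part chiefly concerns how subjects already stopped under 6.9 were followed and censored.

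**What to change.** - **Follow-up.** State in 6.9 that, after discontinuation under that section, disease assessments continue per Table 12 until confirmed PD, with LTFU contacts in addition or afterwards. State how M-protein values obtained after the procedure are to be interpreted.
- **Treatment.** Reconcile 6.9 with the Table 4 TMA row and the daratumumab rules in 6.2.2.2, so that one rule covers each drug. State whether plasma exchange and plasmapheresis are equivalent. The sponsor must choose the clinical rule; no view is offered here.
- **Reporting.** List the subjects stopped under 6.9 before the primary data cutoff, by arm, with date of last disease assessment and PFS status, so that the effect on the primary result can be seen.

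The cost is a short wording change, a listing from existing data, and a few extra laboratory assessments already scheduled for other subjects who stop before PD.
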